4.5 Analysis of the Quantitative Results from the LumiraDX Assay

All comparisons that were conducted using the qualitative result from the LumiraDX assay will be repeated using the quantitative result using the appropriate modification of the analysis to accommodate a continuous variable. Comparisons to the RightSign and qualitative GenScript results will use the Wilcoxon rank sum test with the 2 groups being determined by the outcomes of the RightSign or GenScript test (i.e., the ranks of the LumiraDX results for positive and negative results for the other assays will be compared). Adjusted analyses will be pursued using linear regression after transformation (e.g., logarithmic), if appropriate. Comparisons of the locally and centrally conducted LumiraDX assay will be conducted using linear regression with adjustments made by the inclusion of relevant covariates. The quantitative result will also be used in the competing risk regression models as a continuous covariate and as a set of indicator variables that represent the quartiles of the distribution of this assay (to avoid the linearity assumption).

Other approaches to dichotomizing the quantitative LumiraDX results will be investigated and assessed. Potential values to use for dichotomizing the results will be based on deciles of the distribution and for each potential threshold the sub-hazard ratio for the impact of baseline serostatus on time to sustained recovery will be computed. An alternative cut-off may be selected if there are substantial differences in the hazard ratios.

5 Protection of Human Subjects and Other Ethical Considerations

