There are a large number of POC antibody tests with an EUA from the FDA available for detection of antibodies to SARS-CoV-2, thereby presenting an opportunity to rapidly determine if a patient has endogenous antibodies, which can then be used for patient management. Under the current EUAs, these tests only produce a qualitative interpretation of serostatus. This limits their ability to be used for participant management as the cut-offs are generally selected to optimize specificity. Optimization of specificity is sensible for an assay designed for large scale screening, where false positives are the primary concern. In contrast, if there is a safety concern associated with administration of nMabs to those who are seropositive, false negatives are the primary concern. Hence, there is interest in studying POC antibody tests that produce a rapid quantitative result so that the operating characteristics of different cut-offs can be investigated. This would inform using other cut-offs for timely patient management.

There are 2 aspects of a POC testing platform of interest when designing a trial that may use such a test for patient management: 1) performance of the POC test in a hospital setting where patients would be consented and screened for enrolment; and 2) the ability of the results from the POC test to reproduce the association of baseline antibody levels with clinical outcomes that has been found with the GenScript assay. While the former will be examined prospectively at clinical sites that enroll patients, the latter will use stored specimens from completed TICO trials for expeditious evaluation of the association of POC test results with major TICO outcomes in the context of treatment with nMabs (e.g., a 90-day composite safety outcome and time to sustained recovery, the primary endpoint of TICO trials). Ideally, one would want to determine if

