3.2.2 Central laboratory

The overall objective of central testing of stored specimens is to understand the impact of baseline serology, as assessed by the POC tests, on outcomes of relevance for the TICO trial. The **primary objective** is to test for an association between the POC test result on stored baseline specimens and the primary efficacy outcome in TICO on a subset of specimens from TICO participants for whom the GenScript assay has result has already been determined. Secondary objectives are as follows:

1. Test for an association between each POC test result on stored baseline specimens and efficacy/safety outcomes in TICO in a case-control design.
2. Compare the POC test results to the GenScript results and other antibody test results such as those from Bio-Rad and Quanterix that have already been obtained for these stored specimens.
3. Select a threshold for the quantitative LumiraDX result to optimize the association between the dichotomized assay result and safety and efficacy outcomes using the stored specimens.
4. Compare the 2 POC platforms to each other and the GenScript result using locally (at each site) and centrally determined POC results.
5. Examine associations between these antibody assays and antigen assays which have already been obtained for the stored specimens.
6. Determine the effect of vaccination and other participant characteristics on the antibody test results.

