4.3 Local and Central POC Test Result versus GenScript cPass Assay

The GenScript assay will also be conducted on the specimens at the central laboratory. The locally and centrally determined POC results will be compared to the GenScript result using McNemar's chi-square test and will be supplemented by 95% CIs for the difference in the probability of testing positive. Investigation of site effects and test performance in subgroups will be pursued as described in Section 4.2.

4.4 Association of POC Test Results with TICO Outcomes: A Nested Case-Control Study of Completed TICO Trials

TICO specimens selected for the case-control study will be shipped from the repository at Advanced Biomedical Labs LLC to the central laboratory for analysis. The Fine-Grey approach to competing risk regression will be used to test for an association between the POC test result and time to sustained recovery while controlling for the parent sub-study effect. A significance level of 0.05 will be used to test the null hypothesis that the regression coefficient associated with the presence of antibodies at baseline is zero. The association between baseline POC test results and time to death will be investigated using Cox models stratified by parent sub-study. The association between baseline POC test results and the primary safety composite at days 5, 28 and 90 will be investigated using logistic regression models that control for parent sub-study.

Finally, data will be pooled from the field test and the stored specimens for all qualitative assays conducted to test for differences. This would include the local POC, central POC, and GenScript results from the field test, the GenScript result for the stored specimens and the POC results for the stored specimens. This analysis will use generalized estimating equations for binary outcomes with effects for the type of assay (3 values), if the assay was conducted locally or centrally, and in which protocol/sub-study the participant enrolled. The association due to the specimen coming from the same person will be accounted for by including this information as a clustering effect in the model. Tests for differences in the assays will be based on the Wald test for the regression coefficients for the assays. No multiplicity adjustment will be made for these tests.

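### Section 4.5 compares LumiraDX cut-offs on time to sustained recovery only, so the safety part of secondary objective 3 goes unanswered and no operating characteristic is reported by cut-off

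*Combined protocol and SAP*

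**What the plan says.** Section 3.2.2 sets the aim in secondary objective 3: "Select a threshold for the quantitative LumiraDX result to optimize the association between the dichotomized assay result and safety and efficacy outcomes". The stored case-control specimens are the material for it.

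Section 2.1 explains why a quantitative result is wanted. Authorised cut-offs tend to favour specificity, which suits screening, whereas "if there is a safety concern associated with administration of nMabs to those who are seropositive, false negatives are the primary concern". A quantitative test is therefore of interest "so that the operating characteristics of different cut-offs can be investigated".

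Section 4.5 gives the only method for choosing a cut-off. On the candidates: "Potential values to use for dichotomizing the results will be based on deciles of the distribution". On the comparison: "for each potential threshold the sub-hazard ratio for the impact of baseline serostatus on time to sustained recovery will be computed". On the decision: "An alternative cut-off may be selected if there are substantial differences in the hazard ratios".

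Section 4.4 covers safety for the point-of-care result as such: "The association between baseline POC test results and the primary safety composite at days 5, 28 and 90 will be investigated using logistic regression". It also plans Cox models for death. Neither is tied to the choice of a LumiraDX cut-off.

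**The concern.** The objective names safety and efficacy, and the rationale names operating characteristics. The method names one efficacy measure. An analyst who follows Section 4.5 to the letter will produce nine recovery sub-hazard ratios and nothing else by cut-off. The report could then recommend a new threshold without showing how that threshold relates to death or the safety composite, or how many GenScript-positive specimens it calls negative. The second omission matters because Section 2.1 gives missed antibody-positive patients, under the condition it states, as the reason for looking beyond the authorised cut-off. The point is about which quantities the cut-offs are compared on, not about the uncertainty that comes from searching over several of them.

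**Working it through.** **1. Aim against method.**

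| Element | Asked for | Planned at each cut-off |
|---|---|---|
| Efficacy | Objective 3, Section 3.2.2 | Yes: recovery sub-hazard ratio, Section 4.5 |
| Safety composite, days 5, 28, 90 | Objective 3 (safety outcomes); modelled in Section 4.4 | No |
| Death | Modelled in Section 4.4 | No |
| False-negative and false-positive shares | Operating characteristics, Section 2.1 | No |

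**2. Could another provision fill the gap?** Two candidates stand in Section 4.5.

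- Its opening sentence says: "All comparisons that were conducted using the qualitative result from the LumiraDX assay will be repeated using the quantitative result". This carries the Section 4.4 safety and death models over to LumiraDX as a continuous variable. A slope per unit of signal does not say how one threshold compares with another.
- LumiraDX values are compared between GenScript-positive and GenScript-negative specimens by a Wilcoxon rank sum test. That statistic is equivalent to the area under the ROC curve. It summarises discrimination over all cut-offs and gives no error share at any one of them.

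Neither provides the missing rows.

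**3. The plan's own figures.** Section 3.3.3 gives 90% power at a sub-hazard ratio of 1.91 and 80% at 1.75 with 104 recoveries. The Schoenfeld formula is power = Φ(|ln SHR| × √(D × a × (1 − a)) − 1.96), with D events, a share a seropositive and two-sided 0.05 (sidedness assumed). With D = 104 and a = 0.5:

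- SHR 1.91: 0.647 × √26 − 1.96 = 1.34, power 91.0%
- SHR 1.75: 0.560 × √26 − 1.96 = 0.89, power 81.4%

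At a = 0.46 the results are 90.8% and 81.2%; at a = 0.58 they are 90.3% and 80.4%. The stated figures reproduce and are not in dispute.

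**4. What safety columns could show.** The same approximation gives SE(ln HR) = 1/√(D × a × (1 − a)), and the 95% limits are the estimate divided and multiplied by exp(1.96 × SE). Inputs are 104 recoveries and 20 deaths among 145 participants (Section 3.1). Deciles give nine interior cut-offs, a = 0.1 to 0.9.

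| Cut-off | Recovery SE | Recovery factor | Death SE | Death factor |
|---|---|---|---|---|
| Median | 1/√26 = 0.196 | 1.47 | 1/√5 = 0.447 | 2.40 |
| 2nd or 8th decile | 1/√16.64 = 0.245 | 1.62 | 1/√3.2 = 0.559 | 2.99 |
| 1st or 9th decile | 1/√9.36 = 0.327 | 1.90 | 1/√1.8 = 0.745 | 4.31 |

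Deaths can show whether a cut-off is broadly in line with the recovery result. They cannot rank nine cut-offs. Event counts for the safety composite are not given, so its precision cannot be worked out.

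**5. What GenScript columns could show.** The seropositive share among the 145 is not given. Assuming 46% (the figure for all 320 placebo participants, Section 2.2), there are 145 × 0.46 ≈ 67 GenScript-positive specimens. The widest 95% half-width for a share is 1.96 × 0.5/√66.7 ≈ 12 percentage points. At an assumed 50% it is 1.96 × 0.5/√72.5 ≈ 11.5 points, and at 58% it is 1.96 × 0.5/√84.1 ≈ 11 points. These columns are informative enough to describe a cut-off.

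**The case against.** **The wording is permissive.** A reader might infer that Section 4.5 decides on recovery alone or picks the largest sub-hazard ratio. It does neither: it says other ways of dichotomizing will be looked at and that a different cut-off may be chosen. This objection stands against the stronger reading. It does not close the gap, because recovery is the only outcome named for comparing cut-offs, and the hazard ratios in the decision sentence have no other antecedent.

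**The two aims may coincide.** Section 2.2 reports that lowering the GenScript threshold, so that 58% rather than 46% of 320 participants were seropositive, raised sensitivity and also raised the sub-hazard ratio from 1.45 to over 1.6. This is the only relevant evidence in the documents, and it runs against any forecast that the recovery criterion will produce false negatives. It concerns another assay, so it lowers the stakes without settling the matter for LumiraDX.

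**Tempting numbers.** A reader might note that one decile step moves 14 or 15 of 145 participants and take that as the change in false negatives. Every one of those moved would have to be GenScript-positive, which makes it a worst case and not an estimate. A simulation that always takes the largest recovery ratio also looks alarming. It assumed 145 participants, half antibody-positive, a marker separated by 1.5 to 2.5 SD, 104 events and a simple cohort. The false-negative share exceeded 20% in 37% to 49% of runs at a true ratio of 1.91. But it exceeded 20% in 46% to 52% of runs with no true effect, so the result largely reflects search noise. It also assumes a rule the plan does not state. It is not relied on here.

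**The rationale is conditional.** False negatives come first in Section 2.1 only if there is a safety concern with antibody treatment in seropositive patients. The documents therefore do not support a rule that bars any cut-off with a higher false-negative share. Objective 3, however, names safety without condition.

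**Limits of the data.** The specimens come from placebo participants only (Sections 2.1 and 3.1), so safety associations are prognostic and cannot show harm from treatment. GenScript is the protocol's comparator, not a perfect reference. Both points stand and limit how the extra columns can be read.

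**Conclusion.** The concern holds as a mismatch between aim and method. Of three things called for (efficacy, safety and operating characteristics by cut-off), Section 4.5 plans the first. Followed as written, it leaves the safety part of secondary objective 3 unanswered and reports no operating characteristic at any cut-off.

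The consequence is moderate. One of six secondary objectives of the central-laboratory component is affected. No primary analysis depends on it, and the study's results are not used for patient management. Nothing in the documents shows that a cut-off chosen on recovery would be a bad one. The textual finding rests on no numerical assumption. The precision figures rest on the Schoenfeld approximation in a simple cohort, and on an assumed GenScript-positive share of 46% to 58% among the 145.

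**What to change.** In Section 4.5, add that at each decile cut-off the following will be reported with 95% CIs beside the recovery sub-hazard ratio:

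- (a) the odds ratio for the safety composite at days 5, 28 and 90 and the hazard ratio for death, from the Section 4.4 models;
- (b) the share of GenScript-positive specimens called negative and the share of GenScript-negative specimens called positive.

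State that any alternative cut-off will be put forward in light of these as well as the recovery result, and that the safety columns are descriptive. If the team does not want this, narrow objective 3 to time to sustained recovery so that aim and method agree.

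The cost is a few sentences and one table of 9 × 7 = 63 estimates, of which 9 are already planned. No further specimens or participants are needed. The choice of cut-off becomes less automatic, and the table needs a note that the safety estimates are imprecise and prognostic, and that the shares come from a sample selected on outcome.

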While the semi-quantitative GenScript results do not have any authorization for use in patient management, there is evidence that the use of different thresholds for dichotomizing this semi-quantitative result leads to different estimates of the magnitude of the association between the antibody test and time to sustained recovery. By using a lower threshold for antibody levels and thereby reducing the specificity and increasing the sensitivity for being seropositive, one detects a stronger association. The threshold used for the qualitative result finds that 46% of the 320 participants in the placebo arm are seropositive. If the threshold is lowered so that 58% of the participants are seropositive, we find that the sub-hazard ratio increases from 1.45 to over 1.6.

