A nested case-control study will also be conducted to allow for testing of the association between antibody levels at baseline, as assessed by the POC tests and safety and efficacy outcomes among participants randomized to the placebo group in the bamlanivimab, sotrovimab, and BRII-196/198 trials of TICO. The case definition is death or time to sustained recovery that exceeds 28 days. To maximize the difference between cases and controls, controls are defined as those with a time to sustained recovery of no more than 16 days. With these definitions there are 68 cases and 77 controls for a total sample size of 145. Among these participants, 104 experienced a sustained recovery and 20 died.

Conduct of this nested case-control study will require use of the POC assay on stored specimens. One cannot conduct such tests in a batched fashion which makes this analysis time consuming. This testing will be facilitated by procuring multiple POC platforms at a central location. The use of multiple platforms will allow for multiple tests to be conducted in parallel which is more efficient since each specimen must be run one at a time, and each takes 10-20 minutes.

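### The LumiraDX cut-off search in section 4.5 chooses a threshold and estimates its sub-hazard ratio in the same 145 people, so the ratio of a selected cut-off will be too large, and no correction or uncertainty is planned

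*Combined protocol and SAP*

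**What the plan says.** Secondary objective 3 in section 3.2.2 is to "Select a threshold for the quantitative LumiraDX result to optimize the association between the dichotomized assay result and safety and efficacy outcomes". The same objective assigns this work to the specimens already held from TICO. Section 4.5 gives the method. Candidate thresholds are the deciles of the quantitative result. A sub-hazard ratio for time to sustained recovery is computed at each, and "An alternative cut-off may be selected if there are substantial differences in the hazard ratios". The plan does not say what counts as substantial.

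Section 4.5 does not state the sample size. Section 3.1 describes the stored specimens as "68 cases and 77 controls for a total sample size of 145. Among these participants, 104 experienced a sustained recovery and 20 died". Controls recovered by day 16. Cases died or took more than 28 days. The gap is deliberate: "To maximize the difference between cases and controls".

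Section 4.5 also enters the result "as a continuous covariate and as a set of indicator variables that represent the quartiles of the distribution of this assay". Section 4.4 fits its competing-risk model "while controlling for the parent sub-study effect"; section 4.5 does not say whether the decile models keep that term. The 0.05 level in 4.4 applies to the antibody-presence coefficient, not to the search.

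The motive for other thresholds is in section 2.2. For GenScript, "The threshold used for the qualitative result finds that 46% of the 320 participants in the placebo arm are seropositive". When the threshold is lowered so that 58% are positive, "we find that the sub-hazard ratio increases from 1.45 to over 1.6".

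**The concern.** When several cut-offs are tried on one data set and the one with the strongest association is kept, its apparent ratio contains the luck that made it stand out. Applied to new people, that cut-off will on average show a weaker association.

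The nine decile splits of 145 people are correlated but noisy, so their ratios differ visibly even when nothing real separates them. Section 4.5 gives the reader no means of telling such differences from real ones. The field test cannot serve as validation: it is a single visit, and the data listed in section 3.5 include no recovery outcome.

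What is at stake is later use. Section 2.1 expects the work to inform other cut-offs for patient management, so an inflated ratio could enter the design of a later trial.

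**Working it through.** **Inputs.** From sections 3.1 and 3.3.3: 145 people, 68 cases, 77 controls, 104 recoveries, 20 deaths, GenScript sub-hazard ratio 1.91 in the 145. From section 2.2: 320 placebo participants, ratio 1.45 at 46% positive, over 1.6 at 58% positive. By subtraction, 104 − 77 = 27 cases recovered late and 68 − 27 = 41 did not recover.

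**The plan's own power figure.** For one pre-set cut-off with share q positive, power = Φ(√(104·q(1−q))·ln(ratio) − 1.96). With q = 0.5, √26 = 5.10.
- Ratio 1.91: 5.10 × 0.647 − 1.96 = 1.34, power 0.91 (plan: 90%).
- Ratio 1.75: 5.10 × 0.560 − 1.96 = 0.89, power 0.81 (plan: 80%).

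Both reproduce, but they hold for a single cut-off fixed beforehand.

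**Precision of differences between cut-offs.** SE(log ratio) at percentile p is 1/√(104·p(1−p)): 0.196 at the 50th, 0.200 at the 60th, 0.214 at the 30th, 0.327 at the 10th. For nested splits at p < q the correlation is √[p(1−q)/(q(1−p))], and Var(difference) = SE₁² + SE₂² − 2ρ·SE₁·SE₂.
- 50th v 60th: ρ = 0.816, SE = 0.120, 95% chance limit exp(1.96 × 0.120) ≈ 1.27-fold.
- 50th v 30th: ρ = 0.655, SE = 0.171, limit ≈ 1.40-fold.
- 50th v 10th: ρ = 0.333, SE = 0.320, limit ≈ 1.87-fold.

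The GenScript change that motivates the search is 1.60/1.45 ≈ 1.10-fold. In simulation that pattern becomes an expected log difference of 0.15 in the 145, with SE about 0.12.

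**Simulating the search.** Fine-Gray was fitted as a Cox model with non-recoverers kept at risk to day 90, with nine deciles recomputed in each sample and 6,000 runs per main scenario. New data means an independent sample analysed at the selected threshold value.
- *No association.* The median of largest/smallest decile ratio is 1.65 (1.65 to 1.68 in repeat simulations). The largest ratio averages 1.31, against 1.00 in new data. A 10th or 90th percentile cut gives the largest ratio in 46% of runs.
- *True full-cohort ratio 1.45, step at 46% positive, largest decile always taken.* The apparent ratio is 1.91, against 1.50 in new data of the same design. An outer decile is chosen in 30% of runs.

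**Does changing the cut-off itself lose association?** Ratios in new same-design data:

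| Assumed truth | Searched cut-off | Unchanged cut-off |
|---|---|---|
| Current cut-off is right (ratio 1.45) | 1.50 | 1.71 |
| GenScript pattern of section 2.2 | 1.74–1.77 | 1.76–1.77 |
| Current cut-off far too strict (20% positive; true step at 58%, ratio 1.65) | 1.77–1.78 | 1.50 |

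The first row is a loss, the second no material change, the third a gain.

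**What a bootstrap correction recovers** (1,200–2,000 runs per scenario, 200 resamples each), as apparent / corrected / new same-design data:
- true 1.45: 1.90 / 1.56 / 1.49
- no association: 1.32 / 1.09 / 1.00
- GenScript pattern: 2.21 / 1.81 / 1.77

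It removes about 80%, 70% and 88% of the optimism. The most frequent cut-off receives only about 40% of bootstrap selections, which would show readers how unstable the choice is.

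**The case against.** The search serves one of six secondary objectives and is worded as optional. No error rate is claimed for it. The plan does not rule out confidence intervals for the decile ratios, and elsewhere it reports its main sub-hazard ratios with them. The continuous and quartile models show the dose-response without any search. Section 2.1 explains that authorised cut-offs tend to favour specificity, so there is good reason to look for another.

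Most of this stands, and it limits the point. Intervals at each decile would help, but they would not correct the ratio of a cut-off chosen because its ratio was large. The continuous and quartile models do not correct it either.

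Three stronger readings are tempting, and the documents do not support them.
- A reader might infer that the search makes the cut-off worse. That holds only if the current one is already right; section 2.2 points the other way for GenScript, and the table above shows no material change or a gain in the other cases.
- A reader might infer a flawed comparison between the outcome-selected 145 and the full-cohort 1.45 or 1.6. Section 4.5 plans no such comparison, section 3.1 states the selection openly, and section 3.3.3 supplies a benchmark in the same 145 (1.91).
- A reader might infer that a significance-type rule must govern any change of cut-off. Such a rule, based on the corrected difference, would act in only 1% of runs (95% level) or 6% (80% level) under the GenScript pattern, which would largely defeat secondary objective 3.

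**Conclusion.** The point holds for the reported ratio of a selected cut-off. Following section 4.5 as written would overstate that ratio: about 1.3 against 1.0 with no association, and up to about 1.9 against 1.5 with a true full-cohort ratio of 1.45. The second pair is an upper bound, because it always takes the largest decile. The plan gives readers no measure of this optimism or of the chance spread between deciles. It does not follow that the search is a mistake or that a new cut-off would perform worse. The primary case-control test does not use the searched cut-off. Current care cannot change either, because the quantitative result is not available at the point of care.

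The figures rest on assumptions that the documents do not settle: a step at GenScript's 46% positive (the LumiraDX share is unknown), all 320 eligible so that 320 − 145 = 175 recovered on days 17–28, and no censoring before day 90. Varying them changes little:
- 15% or 30% of the 320 left out for unrelated reasons: 1.86 against 1.46, or 1.80 against 1.40.
- Stratification by three sub-studies: 1.93 against 1.50.
- No association, with 21 of the 41 non-recoverers censored on days 29–90: the spread is 1.64.

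This is a cheap improvement to a secondary analysis.

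**What to change.** Add to section 4.5, before the decile ratios are seen:

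1. Report all nine decile sub-hazard ratios with 95% confidence intervals beside the ratio at the manufacturer's cut-off, keeping the sub-study term of section 4.4.
2. For any selected cut-off, report beside the apparent ratio a bootstrap optimism-corrected sub-hazard ratio that repeats the whole decile search in each resample. Add a bootstrap confidence interval for its difference from the manufacturer's cut-off, and the bootstrap distribution of selected cut-offs. For the interval, use the corrected log difference ± z × the bootstrap SD of the searched difference. With no association its 95% lower limit exceeded zero in 2% of runs, against 10% for a shifted percentile interval.
3. Call any selected cut-off provisional until it is validated in independent data.

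No significance-type rule for changing the cut-off is required.

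The cost is SAP wording and some programming on data already planned. The reported ratio will be less favourable, and some optimism will remain after correction.
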